PIMA1-JO-PR

Adherence and quality of life of CPAP for obstructive sleep apnea: a randomized controlled trial

Protocol ID: PIMA1-3450

Secondary IDs: 3450

Date of the protocol: 14 February 2018

Date of submission to the Ethics and Clinical Research Committee of the Hospital Universitario de La Princesa: March 12, 2018

Research project report

TITLE: *Study on the individualization of a plan to improve adherence based on stratification and the use of telemonitoring for sleep apnea with CPAP.*

Main researcher: [name], [name], [name].

Project type: Individual

Duration: 6 months

Summary (Objectives and Methodology)

Aim: 1 Improve the adherence of patients diagnosed with OSA to CPAP treatment; 2 Follow adhesion; 3 Optimize resources; 4 Comply with SEPAR regulations; Develop experience in telemonitoring along with stratification.

Methodology: Patients with OSA (referral cohort) will be included. All participants will have a diagnosis of OSA with objective tests and a comprehensive evaluation. A follow-up will be carried out with objective evaluation questionnaires and compliance results will be obtained with the measurement of the CPAP hour meter.

List of acronyms in this report

- CPAP- Continuous Positive Airway Pressure (English). Positive Pressure in the Airways (Spanish)
- COPD- Chronic Obstructive Pulmonary Disease
- FEV - Forced Expiratory Volume
- AHI- apnea-hypopnea index
- CHF - Congestive Heart Failure
- mMRC - Modified Medical Research Council. Dyspnoea scale
- PIMA - Individualized Adhesion Improvement Plan
- OSA - sleep apnea-hypopnea syndrome
- SEPAR- Spanish Society of Pneumology
- TM: Telemonitoring

Background section and current status of the issue

OSA is characterized by the appearance of repetitive episodes of obstructive apnea and hypopnea during sleep associated with daytime sleepiness. The severity of OSA is evaluated and classified according to the number of apneas and hypopneas per hour of sleep (apnea-hypopnea index-AHI). In our country, in a prevalence study carried out more than 10 years ago, it was estimated that 15-20% of the population suffered from OSA. The natural history of OSA is still poorly understood, but longitudinal studies show that untreated OSA is associated with increased risk of accidents, loss of quality of life, and increased cardiovascular mortality.

There are few studies on adherence understood as compliance maintained over time and in relation to an awareness of disease and a change in healthy lifestyles; Furthermore, no work has been carried out to address these aspects together with technological advances such as telemonitoring. Of the studies reviewed, the most important conclusions regarding treatment with CPAP are the following:

- Park et al. (2012). This work analyzes the influence of anatomical differences on adherence, which is why they suggest that the examination be incorporated before prescribing. In any case, there is no great impact on adherence as it is the education part, etc.

- Budhiraja et al (2007) and Aloia et al (2007). Long-term adherence is determined by how the results are in the first two weeks.
- Batool-Anwar et al. (2017) studied the influence of the couple, finding that in the first 6 months it is important, although not so much in the long term. It is important to take into account the immediate social support of the patient in order to improve adherence to CPAP.
- Balachandran et al (2013). They found that the patients with the best adherence were those who had a better predisposition and perception of being able to carry out the therapy and its benefits, measured through a simple 6-item questionnaire. The statistical analyzes were regression, and the most important derived result is that the adherence of the patient can be “predicted” based on certain characteristics.
- Hwang et al. (2018) recently carried out a randomized study in which they found that the use of CPAP telemonitoring with automated feedback messages improved 90-day adherence in patients with OSA.

Regarding the educational and training aspects, Olsen et al. Found scientific evidence applying an educational program for new patients. The methodology used was the motivational interview. The detailed contents of each session of said intervention are based on the work of Miller and his colleagues (Miller, Zweben, DiClemente, and Rychtarik, 1995) but with modifications directed to sleep apnea pointed out by Aloia, et al., 2004).


HYPOTHESIS

The stratification / segmentation of the patient allows the elaboration of an individualized plan to improve adherence to treatment with CPAP, using telemonitoring for a specific profile; this stratification improves adherence to CPAP treatment of sleep apnea.

OBJECTIVES

Main goal:

- Improve adherence to CPAP treatment. To measure this variable, the definition of adherence / compliance with SEPAR is taken as a criterion: 3.5 hours per night.

Secondary objective:

- Identify the characteristics of patients that influence the development of their CPAP treatment plan.
- Develop an individualized plan to improve adherence based on the patient's profile and personal characteristics.
- Use telemonitoring for patients at risk of low adherence to improve compliance.

EXPECTED RESULTS

- Adherence is multidimensional and this implies the development of an individualized plan. (Rotenberg, Murariu, Pang, 2016; Sawyer, Gooneratne, Marcus, Ofer, Richards, Weaver, 2013; Ibarra, Morillo, Rudi, Ventura, Navarro, 2013).
- Adherence improves when patient characteristics, disease characteristics, technological factors, clinical factors such as side effects, psychological factors, and social factors are taken into account. (Rotenberg, Murariu, Pang, 2016)
- Influence on adherence to mood, perception of self-efficacy and expectations. (Orruño, Asua, 2016).
- The actions carried out at the beginning of treatment are key to improving adherence. (Orruño, Asua, 2016; Rotenberg, Murariu, Pang, 2016).
- Educational actions improve adherence results, without negative effects. (Rizk AK, Wardini R, Chan-Thim E, Bacon SL, Lavoie KL, Pepin. 2015)
- Support and follow-up measures such as protocolized telephone follow-up and telemonitoring improve adherence. (Ruiz-López, 2009; Rotenberg, Murariu, Pang, 2016)
- The Adhesion Improvement Plan based on a cost-effectiveness balance achieves better adherence results. (Ibarra, Morillo, Rudi, Ventura, Navarro, 2013).

METHODOLOGICAL SECTION

1. Design. Experimental, prospective and controlled study. All participants will sign informed consent after knowing in depth the objectives, methods and risks of the study. The CONSORT Criteria for non-pharmacological trials will be followed (Boutron, Moher, Altman, Schulz & Ravaud, 2008).

2. Sample size: The sample size is defined by the research design, in which the subjects are randomly distributed to the two experimental conditions, that is, the Control Group and the PIMA Group. It is thus necessary to determine at the beginning the minimum size of the groups based on the following factors. Taking into account that the intervention process is based on the motivational interview, in the first place, we establish a type I error of 0.05, and a type II error of 0.20 (power = .8), as is usually assumed in research in the framework of the study of the therapeutic efficacy of motivational / psychological interventions (Hair, Anderson, Tathan & Black, 1999). On the other hand, reviews of previous research on the efficacy of motivational / psychological interventions on the outcome variables to be considered (behavioral change / adherence, quality of life), revealed that there are hardly any studies of this nature, without detail data on standardized effect size that serve as a starting point in defining, among other aspects, the ideal sample size for our research. Due to the characteristics of the existing studies (Edelman, Bell and Kidman, 1999; Edelman, Lemon, Bell and Kidman, 1999; Goodwin et al. 2001), we observed effect size values around 0.50. In addition, for a study such as the one proposed in this study, a sufficient number of subjects is required to allow observing and assuming the normality of the scores in the variables considered, as well as performing multivariate analyzes, with a sufficient number of observations to carry them out.

[figure not shown]
finished. For all the above considerations, we conclude that around 33 subjects per group would be the size of the sample necessary to assess the therapeutic efficacy of the interventions developed. On the other hand, we take into account the type of patient we are dealing with, who may be abandoned, for which a number of 35 subjects per group is established (anticipating a certain experimental mortality). The design effect size as defined is $d = 0.60$, which is a moderate effect size.

3. Stages of the study:

3.1. Referral / recruitment phase and randomization. In patients diagnosed with OSA, 2 groups of at least 35 patients will be constituted. Following the CONSORT Criteria (Boutron, Moher, Altman, Schulz & Ravaud, 2008) for non-pharmacological trials, the randomization method has been selected through a simple method: each time the prescribers evaluate the sleep test, they include in one of the two groups according to the following randomization algorithm: each patient is assigned to a group alternatively, that is, one patient is assigned to the Control group and the next to the PIMA group; This sequence is followed in 6 pairs, being that the following 6 pairs were assigned starting with one patient to the PIMA group and another to the Control group later. This allocation mechanism is also the one used to compensate for experimental mortality in both groups. In this way 2 groups will be configured:

- 1) Control Group or PIMA 0, which will start treatment with regular CPAP WITHOUT stratification;
- 2) PIMA 1 Group, which will start treatment according to stratification; This will be the result of a comprehensive initial evaluation and the result of stratification.

3.2. **Stratification process:** To achieve stratification, two types of variables are taken into account that the bibliography indicates influence the treatment of CPAP: personal variables and modulating variables. Personal variables are those that refer to patient characteristics. These are grouped into 4 categories: protective factors, risk factors, clinical factors and motivation (in the case of OSA). The following figure shows the set of variables used for patient stratification, and their relationship with individualized protocols.

Regarding the modulating variables, these refer to the characteristics of both the patient's environment (distance between the patient's home and the hospital) or relative to options and

preferences of the service (use of app, email; preference for home visit or in consultation, etc.)

The modulating variables that are taken into account for stratification are:

Pro file	Age	Socio-Cultural Level	Accessibility	Technologies 2.0	2.0 Mobility
a	≤50 years	High	Isocrhone ≤20 min	Use app, email, internet	Registration: Punto Inspira, accepts postal shipments
b	>51 years	Medium	Isocrhone >20<40 min	Use internet, with or without email	Media: Punto Inspira, can accept postal shipments
c	>70 years	Low	Isocrhone ≥40 min	Not use of app, internet, email	Low: No Punto Inspira or accept postal shipments

For personal variables, the Perceived Competence Evaluation Questionnaire is used, and the Epworth Scale Test and the Motivation Initial Assessment Questionnaire. This questionnaire has "predictive" capacity. Through this questionnaire, we know if the patient has assimilated the necessary knowledge to start therapy, information and knowledge of the disease, information and knowledge about the treatment, perception of the benefits of the therapy team, clinical stability, compliance with other treatments, social support, bad eating habits, bad exercise habits, sedentary lifestyle, tobacco and / or alcohol consumption and social problems.

With the information from the initial questionnaire and the identified profile, the healthcare provider calculates the stratification label that will determine the best treatment plan for each patient. The clinical situation of the patient is taken into account at all times. The components that determine the patient segmentation label and that will involve the development of a treatment plan or another are: type of diagnosis of OSA (mild, moderate, severe), AHI of the sleep test, patient profile, level of patient motivation, scores obtained in the questionnaire in general and the score obtained in the Epworth test. The results can be:

- High adherence
- Moderate Adhesion
- Low Adherence

Regarding telemonitoring, it is used in patients who in stratification have obtained a label of low adherence:

- The patient who is telemonitored must sign their consent for said procedure to be carried out.
- The monitoring parameters are:
 - o IAH
 - o Leakage (loss of air from the sides of the mask)

[figure not shown]
To know these parameters, the CPAP provider's platform will be accessed, which includes telemonitoring. In this case it is PHILIPS, and the platform is EncoreAnywhere.

The monitoring and visualization of the alerts will be carried out with a determined periodicity: Day 10, Day 20, Day 30 of the period after low adherence detection. The alerts (situations that imply poor evolution and need to notify the prescriber) are the following:

- - Hours <4
- AHI> X + Hours <4
- IAH> X + Hours> 4
- Leaks> Y

Prescribing physician information report: a report is extracted in PDF format that is reported to the prescribing physician.

3.1. Monitoring and control of adherence. All measurements will be performed in 4 times: Day 1 - Day 30 - Day 60 - Day 90 – Day 180. In the Control Group, the usual methodology of treatment with CPAP will be used. In PIMA 1 Group, the methodology will be used according to the Individualized Adherence Improvement Plan arising from stratification.

3.2. Analysis of results.

Descriptive variables (characterize the sample used and make the study replicable and transparent, thus contributing to generalization). Study of initial homogeneity: categorical variables (χ^2) + associated effect size. Quantitative variables: Student's t test for independent samples, correction (Levene's test).

- Hypothesis:
 - T-tests of means of related samples (to know if through the different interventions there are improvements in adherence and quality of life, they report the effects on the outcome variables)
 - Model of structural equations (to know the relationships between protection and risk factors and educational, training and technological actions)

- Independent samples t-test (know the significance associated with the differences between the two interventions)
- Analysis of variance (ANOVA) (differences were due to the type of intervention in combination with some other categorical variable)
- Linear correlations (know the interrelation between the so-called gains or aspects of change of the 2 interventions)
- Effect size:
 - or (Cohen's $d = t / rN$) (value exceeds 0.30, which is equivalent to a moderate-high effect size, greater in any case than 0.60)

3.1. Subjects of study.

Inclusion criteria: Being over 18 years of age, OSA diagnosis for whom CPAP treatment has been prescribed)

Exclusion criteria:

- Hypoventilation obesity
 - severe COPD
 - (FEV1 (%) = <50%)
 - mMRC > 2
 - Cognitive disorders
 - ICC (NYHA: Grade III and IV)
 - or reject

4. Variables

- **Sociodemographic variables:** age, gender, marital status, educational level, ...
- **Clinical variables:** No. hours of CPAP use, IAH (TM), Leakage (TM), side effects.
- **Independent variables:** Stratification / Segmentation vs "SEPAR" Model.
- **Dependent variables:** adherence, quality of life.
- **Modulating variables:** PROFILE, protective factors, risk factors, motivation

ETHICAL ASPECTS AND MEASURES TO MAINTAIN THE CONFIDENTIALITY OF THE DATA

The prescribers and healthcare personnel participating in this Study undertake not to disclose in any way to third parties or to use Confidential Information of patients outside the study. Confidential Information shall be understood to be information that, regardless of its physical or digital medium or otherwise, is confidential (whether or not it is indicated therein or is derived from its nature) to the extent that:

1. is secret in the sense that it is not, as a body or in the precise configuration and assembly of its components, generally known or easily accessible to persons introduced into the circles in which the type of information in question is normally used;
2. has a commercial value because it is secret; and
3. has been subject to reasonable measures, under the circumstances, to keep it secret, taken by the person who legitimately controls it

The execution and development of the Study will give rise to access by healthcare personnel and prescribers to personal data of natural persons, especially patients, responsibility of the Hospital. That is why all of them expressly undertake to treat such data in compliance with the provisions of Organic Law 15/1999, of December 13, on Data Protection and other regulations that modify or develop this matter, and as of December 25 May 2018, in Regulation (EU) No. 2016/679, of April 27, 2016, guaranteeing the security, confidentiality and integrity of personal data that may be accessed or subjected to treatment within the framework of This studio.

The registration of the information will be carried out following the procedure of the Hospital Universitario de La Princesa, that is, all indications derived from internal regulations will be respected. The participants of this Study undertake to keep the strictest reserve and confidentiality regarding the Personal Data accessed during the execution of the Project work.

The main researchers undertake to implement the appropriate technical and organizational measures, in accordance with article 32 of the RGPD, to guarantee the security of Personal Data.

The principal investigators of this Study guarantee that all the participants have assumed generic confidentiality obligations regarding the information they access in the performance of their duties.

SCHEDULE

Activity / Task

Recruitment, constitution of study subgroups, obtaining clinical and functional information, clinical review of participants.

J	F	M	A	M	J	J	A	S	O	N	D
				X	X	X	X				

Activity / Task

Comprehensive evaluation of patients. Educational process. PIMA identification.

J	F	M	A	M	J	J	A	S	O	N	D
				X	X	X	X	X			

Activity / Task

Cross-sectional analysis of results

J	F	M	A	M	J	J	A	S	O	N	D
								X	X		

Activity / Task

Longitudinal analysis of results

J	F	M	A	M	J	J	A	S	O	N	D
									X	X	X

EXPERIENCE OF THE RESEARCH TEAM ON THE TOPIC

The clinical team of Hospital Universitario La Princesa maintains a specific and continuous care activity, being a reference in the area for the treatment of sleep.

VitalAire, Air Liquide Healthcare's therapy activity, has been in home respiratory therapy treatments for more than 30 years.

DIFFUSION PLAN

1) Clinical impact, assistance and / or technological development. This project has a great impact and clinical and technological significance. From a clinical point of view, the aim is to identify the patient in order to better serve him and ensure adherence to one of the treatments where it is more complex to achieve patient compliance.

2) Bibliometric impact. This project is expected to lead to world-class, high-impact publications.

3) Technological development. This project includes the development of computer applications that allow optimization of resources and better assistance.

RESOURCES AVAILABLE TO CARRY OUT THE PROJECT

Consult "Punto Inspira" located in the Hermanos García Noblejas Specialty Center, belonging to the La Princesa University Hospital area.

Resources of VitalAire, concessionary company of home respiratory therapies of the Hospital Universitario de La Princesa: healthcare personnel, computer, telephone, data line, specific applications, transport vehicles, educational material ...

ANEX

Informed consent sheet for the patient complying with the regulations in this regard.

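### At the design effect d = 0.60, 33 per group gives less than the stated 80% power for the between-group t-test: 67% two-sided (70% at 35) or 78% one-sided (80% at 35), and the readable text does not say which applies

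*Combined protocol and SAP*

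**What the plan says.** All of this is in the methodological section of the combined protocol and SAP.

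- Item 2 (Sample size) ties the number to the comparison of the two arms: "The sample size is defined by the research design, in which the subjects are randomly distributed to the two experimental conditions".
- It fixes the error rates: "we establish a type I error of 0.05, and a type II error of 0.20 (power = .8".
- For the effect, it reports from earlier studies of psychological interventions that "we observed effect size values around 0.50".
- It adds a further consideration, that "a sufficient number of subjects is required to allow observing and assuming the normality of the scores in the variables considered", and mentions multivariate analyses.
- It concludes: "we conclude that around 33 subjects per group would be the size of the sample necessary to assess the therapeutic efficacy". Losses are then provided for, "for which a number of 35 subjects per group is established (anticipating a certain experimental mortality".
- The next sentence reads: "The design effect size as defined is $d = 0.60$, which is a moderate effect size".
- Item 3.1 (Referral / recruitment phase and randomization) says that "2 groups of at least 35 patients will be constituted", and that the same allocation mechanism is used to make up for losses in both groups.
- The section on analysis of results assigns the difference between the two interventions to an independent-samples t-test, and change within the interventions to t-tests for related samples.

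The readable text names neither the test behind the number 33 nor its sidedness. In the copy available for review, a figure and part of a sentence just before the conclusion cannot be read, so the answer may stand there.

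**The concern.** A reader who puts these statements together takes the type II error for PIMA versus control to be 0.20 at d = 0.60 with 33 evaluable patients per group. For the t-test that the plan names, this does not follow on either sidedness. The gap is small if the test is one-sided and substantial if it is two-sided.

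The main objective is to improve adherence, and the hypothesis is that stratification does so, so the between-group test carries the trial's message. If that test is two-sided, a true effect of the design size would be missed about one time in three, against the one in five that the plan implies. A non-significant result would then be read as stronger evidence against PIMA than it is.

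**Working it through.** **Inputs.** Alpha 0.05, power 0.80, an effect of about 0.50 from earlier studies, a design effect of d = 0.60, and 33 and 35 per group, all from items 2 and 3.1. The test is the independent-samples t-test of the analysis section, with equal groups. Sidedness is not given, so both are shown. I take d as the standard two-group standardised difference (difference in means divided by the common SD).

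**Formula.** With n per group, df = 2n − 2 and noncentrality λ = d·√(n/2). Power is the probability that a noncentral t with these values exceeds the critical value (for the two-sided test, in either direction).

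**Can 33 be reproduced at d = 0.60?** The normal approximation is n = 2(z_alpha + z_power)²/d².
- Two-sided: 2(1.960 + 0.842)²/0.36 = 43.6, so 44. The exact t calculation gives 44.59, so 45.
- One-sided: 2(1.645 + 0.842)²/0.36 = 34.3, so 35. The exact t calculation gives 35.04.

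Neither gives 33. The one-sided calculation does give 35 to rounding.

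**Power at the plan's numbers, d = 0.60.**
- n = 33: λ = 0.60·√16.5 = 2.437, df = 64. Critical t is 1.998 two-sided and 1.669 one-sided. Power is 67.0% and 77.8%.
- n = 35: λ = 0.60·√17.5 = 2.510, df = 68. Critical t is 1.996 two-sided and 1.668 one-sided. Power is 69.7% and 79.96%.

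**Summary.**

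| Evaluable per group | d | Two-sided power | One-sided power |
|---|---|---|---|
| 33 | 0.60 | 67.0% | 77.8% |
| 35 | 0.60 | 69.7% | 79.96% |
| 45 | 0.60 | 80.4% | – |
| 33 | 0.50 | 51.6% | 64.2% |
| 35 | 0.50 | 54.1% | 66.5% |

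A simulation of 200,000 trials per setting agrees with the rows for 33 and 35 (for example 0.672 and 0.779 at n = 33, d = 0.60).

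**Effect detectable with 80% power.** Two-sided: 0.70 at 33 and 0.68 at 35. One-sided: 0.62 at 33 and 0.60 at 35 (0.6004).

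**Type II error at d = 0.60, against the stated 0.20.** Two-sided: 0.33 at 33 and 0.30 at 35. One-sided: 0.22 at 33 and 0.20 at 35.

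**The case against.** The strongest defence is that the test was meant to be one-sided. The hypothesis is directional, and the sentence giving d = 0.60 comes straight after the one that sets 35 per group. It can be read as the effect that 35 per group detects, not as the input behind 33. One-sided, the detectable d at 35 per group is 0.6004, so the pair (35, 0.60) is reproduced. This stands. On that reading the power at the recruited number is right, and the shortfall at 33, a number the plan itself calls approximate, is about 2 points. What remains is that 35 cannot be both the requirement and 33 plus an allowance for losses. Also, no readable sentence declares a one-sided test.

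Item 3.1 replaces losses and sets 35 as a minimum, so 35 evaluable per group is a plausible working number. This also stands, and it is why both numbers are shown. It does not close the two-sided gap: 35 still gives 70%, and nothing in the text plans for 45.

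The unreadable text may name the test and its sidedness, and its absence from this copy is not a fault of the plan. It could settle which row of the table applies. It could not make 33 per group give 80% at d = 0.60 for this t-test.

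Normality and multivariate analyses are also given as reasons for the size. They can raise a minimum, but they do not supply missing power.

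The effect-size line in the analysis section is garbled, so the meaning of d is an assumption. If that line means t divided by the square root of the total number of patients 2n, then t/√(2n) = d·√(n/2)/√(2n) = d/2. Its two benchmarks, 0.30 and 0.60, then agree with the standard d.

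**Conclusion.** The 33 per group that the plan calls necessary falls short of 80% power for the between-group t-test on either sidedness and at either effect size that the plan mentions. At d = 0.60 the shortfall is 13 points two-sided (80 − 67.0) and 2.2 points one-sided (80 − 77.8). At 35 it is 10.3 points two-sided and nil to rounding one-sided. At d = 0.50 every combination is at 66% or below.

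A reader might infer that the trial simply has 67% power, or that an arithmetic error has been proved. The documents do not support that: they never state a two-sided test, and a one-sided test with 35 evaluable per group matches the plan's own pair. Nor do they say which calculation produced 33, and nothing here rests on a guess about it. What is established is that the stated power holds only for a one-sided test with 35 evaluable per group, and that a reader cannot tell whether this was meant.

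The figures assume the standard two-group d, equal groups and an unadjusted t-test. The point should be fixed. Confidence is medium, because the sidedness is open.

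**What to change.** Keep the sample. In item 2, name the sidedness of the between-group t-test, the effect size it is powered for and the evaluable number per group, and replace the power statement with the matching sentence:

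- Two-sided: with 33 (35) evaluable patients per group, power is 67% (70%) at d = 0.60 and 52% (54%) at d = 0.50; the effect detectable with 80% power is d = 0.70 (0.68).
- One-sided: 35 evaluable patients per group, maintained by replacing losses, give 80% power at d = 0.60; 33 give 78%. At d = 0.50 power is 66% with 35 and 64% with 33.

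If the part of the text that cannot be read here already names the test and its sidedness, only the matching power sentence is needed.

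The cost is protocol wording, with no extra patients. The downside is a less favourable stated power if the test is two-sided: 67% to 70% in place of 80% at d = 0.60. If a one-sided test with 35 evaluable per group was intended, the stated power hardly changes, but 35 must then be described as the requirement and not as 33 plus a reserve.

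### Patients are allocated by a fixed alternation that the prescribers apply themselves, with no random element or concealment, yet the trial is called randomised

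*Combined protocol and SAP*

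**What the plan says.** The title is "Adherence and quality of life of CPAP for obstructive sleep apnea: a randomized controlled trial". The sample size section says that "the subjects are randomly distributed to the two experimental conditions".

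The section on the referral/recruitment phase and randomization then describes the mechanism:

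- Who and when: "each time the prescribers evaluate the sleep test, they include in one of the two groups according to the following randomization algorithm".
- The rule: "each patient is assigned to a group alternatively, that is, one patient is assigned to the Control group" and the next to PIMA.
- The reversal: "This sequence is followed in 6 pairs, being that the following 6 pairs were assigned starting with one patient to the PIMA group".
- Replacement: "This allocation mechanism is also the one used to compensate for experimental mortality in both groups".

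The protocol mentions no random list, generator, envelope, central allocation or independent list holder. It requires informed consent but does not say whether consent comes before or after allocation. It also does not say how the sequence continues after the second set of 6 pairs.

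The stratification section lists the components of the adherence label, among them "type of diagnosis of OSA (mild, moderate, severe), AHI of the sleep test, patient profile, level of patient motivation". The analysis section plans a "Study of initial homogeneity: categorical variables" and quantitative variables compared between the groups, by chi-squared and t tests.

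**The concern.** Alternation is deterministic. The starting arm and the point of reversal are both fixed in advance, so the reversal adds no randomness. Whoever applies the rule has to know the position in the sequence, and therefore knows the arm before the patient is included.

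Here that person is the prescriber, who has just read the sleep test. Its AHI and severity are components of the protocol's own prediction of adherence, and adherence is the main outcome. A prescriber who knows the next arm could include a patient, defer the patient, or judge the patient unsuitable with that knowledge. The bias could favour either arm.

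The exclusion list leaves room for this: cognitive disorders carry no threshold, and refusal counts as an exclusion. A causal reading of the comparison between arms depends on how patients entered them, and no later analysis can restore randomisation.

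**Working it through.** **1. The rule written out.** With C for Control and P for PIMA, the text defines 24 assignments:

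CPCPCPCPCPCP PCPCPCPCPCPC

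This gives 12 C and 12 P. Every pair holds one patient of each arm, so 70 patients give 35 and 35, which matches the planned group size. The rule balances numbers but makes no assignment random.

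**2. Predictability.**

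- Knowing the rule and the position: 24 of 24 (100%).
- Knowing only the last arm and guessing the opposite: wrong only at patient 13, so 22 of 23 (96%).
- If the 24-patient cycle repeats to 70 (an assumption): wrong at patients 13, 25, 37, 49 and 61, so 64 of 69 (93%).
- Unrestricted 1:1 randomisation, for comparison: 50% on average.

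**3. What an imbalance would do (illustration).** The documents give no figure for a prognostic imbalance, so I assume a bias of d = 0.10 to 0.20 SD of the outcome. For the planned independent-samples t test with n = 35 per arm, df = 68 and two-sided 5%, the noncentrality is d × √(35/2) = 4.183 × d. The probability of rejecting when there is no true effect is:

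| Assumed bias (SD) | Noncentrality | Rejection |
|---|---|---|
| 0.10 | 0.418 | 7.0% |
| 0.15 | 0.627 | 9.5% |
| 0.20 | 0.837 | 13.1% |

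**4. Whether the homogeneity tests would see it.** If the bias comes through one measured covariate with correlation r to the outcome, the imbalance in that covariate is d / r. The same t-test formula gives the chance of a significant baseline test:

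| r (assumed) | Bias d | Covariate imbalance (SD) | Flagged |
|---|---|---|---|
| 0.5 | 0.10 | 0.20 | 13% |
| 0.5 | 0.20 | 0.40 | 38% |
| 0.3 | 0.10 | 0.33 | 28% |
| 0.3 | 0.20 | 0.67 | 79% |

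An unmeasured factor would not be flagged at all, and flagging does not correct the bias. The planned ANOVA adds one categorical variable that is not named.

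**5. What a blocked random list would give.** Suppose someone tracks all past assignments and always guesses the arm that is behind. The expected share correct is 75.0% in blocks of 2, 70.8% in blocks of 4 and 68.3% in blocks of 6. With the three sizes equally likely, the long-run share is (2 × 0.750 + 4 × 0.708 + 6 × 0.683) / 12 = 70.3%. In 20,000 simulated lists of 70 patients it was 70.1%. The arms were equal in 81.3% of lists, differed by 2 in 18.7%, and never differed by more.

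**The case against.** The strongest reply is that predictability is not bias. If every eligible patient entered in order of arrival, there would be little to steer, and the text can be read as consecutive entry. The protocol speaks of prescribers in the plural and does not say who keeps the running position. AHI and severity are only part of the adherence label; the healthcare provider calculates it and also uses motivation, questionnaire scores and the Epworth score. CPAP use is read from the machine's hour meter, which is objective. The baseline comparison covers several variables and reports effect sizes for the categorical ones, so an imbalance could be noticed without a significant test. The SD-based figures rest on assumed values.

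Part of this stands. The documents do not show that selection occurs, the error rates in steps 3 and 4 are illustrations, and the 64 of 69 depends on the cycle repeating. Several baseline tests with effect sizes would also see somewhat more than one t test.

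The rest does not remove the problem. Whoever applies an alternation must know where it stands, and the protocol gives that task to the prescribers. Consecutive entry is not required in so many words, and eligibility, refusal and the decision to prescribe all leave discretion. An objective outcome does not protect against differences in who enters each arm. None of this makes the rule random.

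**Conclusion.** The concern holds. As written, the trial is quasi-randomised: allocation is fully predictable (24 of 24 defined assignments), is applied by the people who include the patients, and is not concealed. The title and the sample size text claim a property that the design lacks. This conclusion rests on the wording of the rule alone.

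The possible damage cannot be measured from the documents. Under an assumed imbalance of 0.1 to 0.2 SD, in either direction, the false-positive rate would be about 7% to 13% instead of 5%, and the baseline tests would often miss the cause. The main comparison depends on allocation, so this should be corrected before patients are enrolled.

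**What to change.** Replace the alternation, including its use for replacing dropouts, as follows:

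- Generate a 1:1 list by computer, in permuted blocks of randomly varying size (for example 2, 4 and 6), and do not disclose the block sizes to the prescribers. The block sizes are a preference; the random sequence and its concealment are the essentials.
- Name a holder of the list who does not enrol patients. The company that owns the PIMA rights also supplies study staff, so the holder should preferably have no part in delivering PIMA either.
- Reveal each assignment, by sequential opaque sealed envelopes or a locked file, only after eligibility and consent are recorded and any baseline measures common to both arms are taken. State this order in the protocol.
- Describe any patients already alternated as quasi-randomised in the title, protocol and report. If both kinds of patient end up in the trial, also show the results separately by method of allocation.

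The cost is a short amendment and minor logistics. The sample size is unchanged, and at 70 patients the arms would differ by at most 2. Blocks do not remove all guessing: about 70% of assignments could still be guessed by someone who tracks every past one, against 100% now.
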